- 1. To assess the separate and combined effectiveness of two components of a cognitive/behavioral intervention that together improve oral hygiene behaviors and oral hygiene status;
- 2. To assess whether differential sequenced combinations of these components has a differential effect on behavioral and clinical outcomes;
- 3. To investigate the mediation effects of cognitive/behavioral factors in changing clinical outcomes.

Primary Outcome Measures: Plaque Scores and Gingival Index

Secondary Outcome Measure: Oral Health Related Quality of Life

Population: Sample size: 360

Gender: Males and Females

Age: Children and adults aged 18-61 with disabilities and those aged 62 and older who meet income guidelines and may have chronic health conditions with quotas of 52 people 62> and 8 people <61 in cycles II and III established by NIDCR in October, 2016

Demographic group: Vulnerable adults or children; we will recruit from low income senior housing in Central Connecticut. Residents must meet income guidelines and be over the age of 62 or be disabled adults or children.

General health status: The participants are independent living older adults residing in low income senior housing. Residents include vulnerable adults over age 21 and individuals meeting the NIH definition of children ages 18-21.

Geographic location: Central Connecticut

Phase: not applicable

Number of Sites: 6 recruitment sites (housing for seniors and disabled

individuals); The University of Connecticut School of Dental Medicine and the Institute for Community Research are

coordinating sites.

Description of Intervention:

The intervention includes two components: 1) a face to face administration of the AMI-PM, a participatory counseling model, and 2) a targeted building-level campaign consisting of up to three half-day oral health events, all based on the study's conceptual model.

Study Duration: 60 months

Subject
Participation
Duration:

[figure not shown]
16-18 months

Estimated Time to

Complete

Enrollment: approximately 36 months

SCHEMATIC OF STUDY DESIGN:

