5.5.2 Handling of Subject Withdrawals or Subject Discontinuation of Study Intervention

The sample size was powered anticipating an attrition rate of 25% which greatly exceeds our experience in the pilot study which was 15%. We do not expect people to withdraw because of adverse effects of the interventions. Once we are certain at any point in time that a participant has withdrawn or has discontinued, we will retain the person in the study up to the point at which they have withdrawn. If they withdraw after T1, we will include them in the T1 comparison. If they withdraw after T2 and before T3, we will include them in the T2 analysis, but exclude them from the T3 sustainability of effect analysis.

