12 STATISTICAL CONSIDERATIONS

12.1 Study Hypotheses

- 1. The AMI-PM will produce better short term (T1) clinical outcomes than the Campaign (CA+PM) (AIM 1).
- 2. The CA+PM+AMI-PM will produce better mid-term (T2) and long-term (T3) clinical outcomes than the AMI-PM+CA+PM (AIM 2).
- 3. The AMI-PM will produce more change in mediating cognitive domains than the CA+PM.
- 4. Both AMI-PM+CA+PM and CA+PM+AMI-PM will result in no differences in change in mediating cognitive domains from T0 to T2.
- The greater the dosage (proportion of total talking points recorded for all domains in a tailored AMI; and exposure to campaign activities and messages), the better the outcomes.
- 6. We will investigate an exploratory hypothesis examining the effects of the intervention and sequence on oral health quality of life (a secondary outcome), as well as on clinical outcomes.

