12.2 Sample Size Considerations

Sample size calculations are based on the primary outcomes of continuous measures of the Gingival Index and Plaque Scores using estimates of effect and variation from the pilot grant. The MFFD design has two sequences, called A:B and B:A, and two periods (1 and 2). We will power on the first period, which is essentially a two-arm parallel design with randomization at the building level. The study design will recruit N=60/building, with 3 buildings on sequence A:B (N=180) and three on sequence B:A (N=180).

Table Sample size for a two-group t-test, using a two-sided α =0.05						
Outcome	Source	Mean	Std Dev	Effect	N per	Power
		difference		Size	group	
Plaque Index	Pilot	0.25	0.34 (pilot)	0.74	123	99
Gingival Score	Pilot	0.66	0.60 (pilot)	1.1	123	99
Plaque Index	Pilot	0.25	0.47 (UCL)	0.53	123	98
Gingival Score	Pilot	0.66	0.81 (UCL)	0.82	123	99
Plaque Index	Pilot*.75	0.20	0.47 (UCL)	0.42	123	91
Gingival Score	Pilot*.75	0.50	0.81 (UCL)	0.62	123	99
UCL= Upper 95% CL of the pilot study SD						

Attrition: Longitudinal studies must account for attrition. If we assume a conservative 75% retention rate across the study that would leave us with approximately N=135 per intervention group, or N=45 per building.

Effects of intra-class correlation (ICC) within sites: The cluster design can sometimes impact the power of a study and our calculations consider this human phenomenon. To account for the cluster design, we calculated the effective sample size which is the sample size used for power calculations, according to Killip et al. With this design we expect to have 6 clusters of N=45 each finish the study, or 135 per sequence. Assuming an intracluster correlation coefficient (ICC) of 0.01 or 0.02, which are typical values for human subject studies, this gives effective sample sizes closer to 123. The strategy therefore is to accordingly adjust the sample sizes used in calculations. As a result, our sample size calculations are based on a maximum number of N=123 per intervention (not 135) after accounting for loss of power due to intra-class correlation. Using N=123 per group, our power ranged from 91 to 99 for different scenarios reflecting varied assumptions, as shown in the attached memo from September 5, 2016.

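### Two unranked primary outcomes, compared at T1 and again at T2 and T3, with no success rule, no multiplicity control and no stated test level after T1

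*Combined protocol and SAP*

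**What the plan says.** The protocol summary lists "Primary Outcome Measures: Plaque Scores and Gingival Index". Sections 3.2.1 and 4 agree; no composite is defined and neither outcome is placed first.

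Section 12.1 states two directional hypotheses on clinical outcomes:

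- Hypothesis 1: "The AMI-PM will produce better short term (T1) clinical outcomes than the Campaign (CA+PM) (AIM 1").
- Hypothesis 2: "The CA+PM+AMI-PM will produce better mid-term (T2) and long-term (T3) clinical outcomes than the AMI-PM+CA+PM (AIM 2").

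The only significance level in the documents heads the section 12.2 table: "Sample size for a two-group t-test, using a two-sided" α of 0.05. Each outcome row uses it in full. Its scope is the first period: "We will power on the first period, which is essentially a two-arm parallel design with randomization at the building level".

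Section 12.4 assigns Hypothesis 1 to standard two-arm methods and Hypothesis 2 to repeated measures models in which contrasts between time points may be built. It fixes neither their number nor their level. Section 5.5.2 treats T2 and T3 as separate analyses: for a participant who leaves between them, "we will include them in the T2 analysis, but exclude them from the T3 sustainability of effect analysis".

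Neither section 12.2 nor section 12.4 gives a multiplicity adjustment, a testing order, or a rule for when a hypothesis counts as supported.

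**The concern.** With two primary outcomes, Hypothesis 1 offers two ways to reach significance. With two outcomes at two visits, Hypothesis 2 offers four. If one success is enough and each test is run at 0.05, the error rate for the hypothesis as a whole is above 5%.

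The gap also affects interpretation. If plaque improves and gingival status does not, or a sequence effect appears at T2 and not at T3, the plan does not say whether the hypothesis is supported. The decision would then be made after the results are known, on the trial's first two aims.

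**Working it through.** **Inputs from the documents.** Two primary outcomes (protocol summary). T1 for Hypothesis 1; T2 and T3 for Hypothesis 2 (12.1). Two-sided 0.05, 123 per group, and conservative rows of 0.20/0.47 for plaque and 0.50/0.81 for gingival (difference/SD, 12.2). 135 completers per group in clusters of 45, ICC 0.01 or 0.02 (12.2).

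**Assumed, not in the documents.** Correlations of 0 to 0.7 between outcomes and between visits; 0.05 per test at T2 and T3; any single significant result counts; each single test holds its nominal level.

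**Step 1: reproduce the plan's power.** Two-sample t-test with noncentrality δ / (σ√(2/n)) and 244 degrees of freedom.

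- Plaque, conservative row: 0.20 / (0.47 × √(2/123)) = 3.34, power 91.4% (plan: 91).
- Gingival, conservative row: 0.50 / (0.81 × √(2/123)) = 4.84, power 99.8% (plan: 99).

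The other four rows also reproduce to within 2 points.

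**Step 2: chance of at least one false positive.** With k independent tests at 0.05 this is 1 − 0.95^k:

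- k = 2: 1 − 0.9025 = 9.75%.
- k = 4: 1 − 0.8145 = 18.5%.

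Counting only results in the hypothesised direction, each test contributes 0.025: 1 − 0.975² = 4.9% and 1 − 0.975⁴ = 9.6%.

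Simulation of correlated normal statistics (2 million draws) gives:

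| Correlation (outcomes / visits) | H1, either direction | H1, hypothesised direction | H2, either direction | H2, hypothesised direction |
|---|---|---|---|---|
| 0 / 0 | 9.8% | 4.9% | 18.6% | 9.7% |
| 0.3 / 0.3 | 9.5% | 4.8% | 17.7% | 9.0% |
| 0.5 / 0.5 | 9.1% | 4.6% | 16.1% | 8.1% |
| 0.7 / 0.7 | 8.3% | 4.2% | 13.7% | 6.9% |

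Only the between-outcome correlation matters for Hypothesis 1. If Hypothesis 2 were one sequence contrast per outcome, it would have two tests and the Hypothesis 1 column would apply.

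**Step 3: power at 0.025 on the plan's own table (N=123).**

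- Plaque, conservative row: 91.4% to 86.0%.
- Plaque, full pilot difference with upper-limit SD: 98.6% to 97.2%.
- Gingival, conservative row: 99.8% to 99.5%.

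**Step 4: sensitivity to the effective N.** The usual design effect, 1 + (45 − 1) × ICC, does not give 123:

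- ICC 0.01: 135 / 1.44 = 94 per group.
- ICC 0.02: 135 / 1.88 = 72 per group.

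The conservative plaque row then goes from 83% to 74% at 94 per group, and from 72% to 61% at 72 per group.

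**The case against.** The strongest reply is that the inflated rates depend on a decision rule the plan never states. Four parts of it deserve weight.

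- A reader might infer that T2 and T3 are also planned at 0.05. The documents do not say so: the only level belongs to a table restricted to the first period. This stands, and 0.05 at later visits is an assumption here.
- A reader might infer that, as written, any one p-value below 0.05 supports the hypothesis. No such rule appears. The wording of Hypothesis 2 joins T2 and T3 and can be read as requiring both. If every component had to succeed, nothing would be inflated. This stands as a limit on the percentages. It does not close the gap, because no all-must-succeed rule is written either.
- Both hypotheses are directional, so a significant result the wrong way would not support them. In the hypothesised direction Hypothesis 1 stays at 4.2-4.9%, and Hypothesis 2 is about 7-10%. This stands. The two-sided figures are the ones that match the table's two-sided α.
- Four tests for Hypothesis 2 is an inference, since section 12.4 leaves contrasts optional. Section 5.5.2 makes separate T2 and T3 analyses plausible but does not fix them.

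Nor does the plan promise a 5% family-wise rate. Its 0.05 is a per-test level for sample size, so the percentages do not show a stated guarantee being broken.

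**Conclusion.** The concern holds as an omission. There are two unranked primary outcomes and repeated time points; the T1 planning table gives each outcome the full 0.05; and there is no later test level, adjustment, order or success rule.

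Its size is conditional. If any one result counts and each test is at 0.05, the either-direction error is about 8-10% for Hypothesis 1 and 14-18.5% for Hypothesis 2, or 8-10% for the latter with one contrast per outcome. In the hypothesised direction the rates are about half. The correlations are assumed. The figures also take each single test as valid. Section 12.4 describes correlation within a person but not within a building, so the true rates could be higher.

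The plan should settle this before results are seen. It calls for no change to recruitment, visits or treatment.

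**What to change.** Add to section 12.4:

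> Within each of Hypotheses 1 and 2 the family-wise error is 5%. At T1 plaque and gingival p-values are compared by Holm. For Hypothesis 2 each outcome is tested at 0.025 at T2, and at T3 at 0.025 only if that outcome was significant at T2. Each hypothesis is supported only for the outcomes and visits that pass.

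Show the section 12.2 table at 0.025 as well.

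**Why it holds 5%.** For Hypothesis 2 each outcome is a fixed sequence at 0.025, so the two together cannot exceed 0.025 + 0.025 = 0.05. Simulation agreed in every scenario run. Holm at T2 with T3 tested at whatever level the outcome was rejected would look natural, but gave about 6.5-7.4% when both T2 effects were real and both T3 effects null, or when only one T2 effect was real.

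**Cost.** The change is wording, but it has two costs.

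- Power: at N=123 the conservative plaque row falls from 91% to 86% at 0.025, while gingival stays above 99%. At T1 that is the worst case, because Holm tests plaque at 0.05 once gingival has passed. The loss is larger at the smaller effective sizes in Step 4.
- Scope: a sequence difference that appears only at T3 could not be claimed as confirmatory, although section 12.1 hypothesises one there.

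**Alternative.** Declare that both outcomes must succeed. That also removes the inflation. On the plan's conservative rows at T1, joint power is at least 91.4% + 99.8% − 100% = 91.2%, but a real effect on one outcome alone would not support the hypothesis.

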4 STUDY DESIGN

Overall Design: The study utilizes a modified fractional factorial design (MFFD) which compares the short term outcomes of the two intervention components: the tailored individual level brief intervention (AMI-PM) and the group level Campaign including embedded oral health skills development through practice-to-mastery (CA+PM). It also evaluates the effects of differential sequencing of these modes of delivery components in relation to short and longer term outcomes. Finally, it evaluates intervention mechanisms through mediational modeling of the cognitive and the behavioral components over time. The two intervention components are the individualized AMI-PM (Component A), and the group CA+PM (Component B). To evaluate sequencing we will randomize pairs of senior residences into two conditions: Condition 1 and Condition 2. Buildings in Condition 1 will initiate with Component A, followed by Component B. Buildings in Condition 2 will initiate with Component B, followed by Component A. This study design will allow us to compare the AMI-PM outcomes to CA+PM short term outcomes, and to determine which condition sequence (A+B or B+A) will produce the best clinical outcomes. Each of 3 cycles of Condition 1 (A+B) compared to Condition 2 (B+A) will take place over a 16-18 month period each in two matched buildings with an N of 60 per building (N per cycle of 120; total N for all three cycles approximately 360). We anticipate an attrition rate of approximately 25% and a final N of approximately 270 by the T3 measure, 135 in Condition 1 and 135 in Condition 2. Primary outcomes are improvements in gingival health and decreases in plaque scores.

A description of the study population: Participants will be recruited from low income senior housing in Central Connecticut. The population consists of independent living older adults many of whom have chronic health conditions. Residents also include adults less than 62 years of age residing in these buildings who are disabled. Residents must meet income guidelines and be over the age of 62 or be disabled children and adults between the ages of 18 and 61.

Methods for collecting data for assessment of study objectives: Data collection will consist of clinical assessment, and surveys evaluating changes in cognitive domains (See Section 16).

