Calculation for Primary Outcomes: While the pilot data provide a good starting point for sample size estimation, we acknowledge that the study was small and the results provide only estimates. To be conservative regarding pilot results, we 1) decreased the observed effect size by 25% and 2) used the upper 95% CL of the standard deviation for calculations. Employing these two hedges gives protection and helps assure we will have sufficient power to detect similar (or smaller) effect sizes with 80% power. With N=135 per group our study still has more that 90% power to find detect the mean differences (MD) in the table below.

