To test hypothesis #4, we will conduct dynamic mediation using latent change (difference) score (LCS) mediation analysis. The analyses will be conducted in Mplus 7 where change (difference) scores representing differences in each mediator and outcome variable from baseline to final follow up (i.e. T1-T0 (ΔT_{10}), and T2-T1(ΔT_{21}) will be generated. It is the difference scores of the mediators and outcome variables that are modeled. Generally speaking, causal paths specifying latent (true) change, represented by change in knowledge, oral health beliefs/norms, OH social support, oral hygiene behaviors, fears/worries, oral health practice to mastery skills, and behavioral intentions in going from T0 to T1, and T1 to T2 will be specified, to predict change in Gingival Index and Plaque Scores at T2 (i.e., ΔGingival Index₂₁, ΔPlaque score₂₁). For example, we will test whether change in fears/worries from T0 to T1 significantly predicts changes in Gingival Index and Plague Scores at final follow-up, T2 (ΔGingival Index₂₁, Δ Plague scores₂₁). To assess the impact of the change in self-efficacy (Δ SE). on changes in Gingival Index scores (ΔGingival Index), direct and indirect paths from change in self-efficacy from baseline to first follow up (ΔSE₁₀) that predict the change in Gingival Index at the final follow-up (ΔGingival Index₃₀) will be specified and tested. Select direct and indirect paths from change scores of the other mediator variables to change scores of behavioral outcomes will also be specified in a similar fashion, and all these relationships will be tested simultaneously.

Summary: Using a conservative set of assumptions and based on our own pilot data, we have demonstrated, using our pilot data estimates, that we will have sufficient power to detect significant changes, using a two-group t-test which makes minimal

IRB Review
IRB NUMBER: 14-188-6
IRB APPROVAL DATE: 01/03/2019
12/14/2018

Good Oral Health: A Bi-level Intervention to Improve Older Adult Oral Health Protocol #14-046-E

assumptions about the data. It is worth noting that the proposed statistical models have greater power characteristics than the t-tests used to calculate power.

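### The effective sample size of 123 per arm does not follow from 45 completers per building and an ICC of 0.01 or 0.02 (it is 94 or 72), so the stated power of 91–99% should read about 72–99%

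*Combined protocol and SAP*

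**What the plan says.** Section 12.2 powers the trial on the first period, a two-arm comparison of buildings randomised to AMI-PM or CA+PM, using a two-group t-test at two-sided 0.05. It recruits 60 per building, three buildings per arm, and allows for 25% attrition: "With this design we expect to have 6 clusters of N=45 each finish the study, or 135 per sequence". It then adjusts for clustering, taking an intracluster correlation ("ICC) of 0.01 or 0.02, which are typical values for human subject studies, this gives effective sample sizes closer to 123"). All six rows of the table use 123 per group, and the section concludes: "Using N=123 per group, our power ranged from 91 to 99 for different scenarios reflecting varied assumptions".

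The next paragraph, on the primary outcomes, cuts the pilot effect by 25% and takes the upper confidence limit of the SD. It says these hedges help secure "sufficient power to detect similar (or smaller) effect sizes with 80% power", and adds: "With N=135 per group our study still has more that 90% power". The summary that closes Section 12.4 states that "the proposed statistical models have greater power characteristics than the t-tests used to calculate power".

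**The concern.** Section 12.2 gives every input to the clustering adjustment, and the answer it prints is not the one those inputs produce. A drop from 135 to 123 is a loss of about 9%, which is far too small for groups of 45 at an ICC of 0.01 or 0.02.

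This section is the plan's only justification that Hypothesis 1 can be answered on Plaque Score and Gingival Index. It presents 123 as already allowing for intra-class correlation, so a reader would take clustering as covered when most of its cost has been left out.

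Two other statements compound this. The claim at 135 per group carries no clustering adjustment, although the preceding paragraph says that 135 is not the number to use. The claim that the planned models are more powerful than the t-tests has no calculation behind it.

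**Working it through.** **Inputs (Section 12.2).** 135 completers per arm; cluster size m = 45; three buildings per arm; ICC 0.01 or 0.02; two-sided alpha 0.05; differences and SDs from the power table.

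**Step 1: reproduce the table at 123.** Noncentral t, effect d = difference/SD, df = 2n − 2. At n = 123, plaque 0.20/0.47 gives 91.4% (stated 91), plaque 0.25/0.47 gives 98.6% (stated 98), and gingival 0.50/0.81 gives 99.8% (stated 99). The other three rows exceed 99%. The power method is therefore the plan's own, and only the sample size is in question.

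**Step 2: effective sample size.** The design effect is 1 + (m − 1) × ICC.
- ICC 0.01: 1 + 44 × 0.01 = 1.44; 135/1.44 = 93.75, about 94.
- ICC 0.02: 1 + 44 × 0.02 = 1.88; 135/1.88 = 71.8, about 72.

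**Step 3: can 123 be recovered?**
- ICC implied by 123: (135/123 − 1)/44 = 0.0022, about one-fifth of the lower ICC assumed.
- No attrition, 60 per building: 180/1.59 = 113 or 180/2.18 = 83.
- Both arms together (270): 187.5 or 143.6.
- Number of clusters (6) used in place of cluster size, ICC 0.02: 135/(1 + 5 × 0.02) = 122.7. This matches but is not a valid design effect here. It may be where 123 came from; the documents do not show the derivation.

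**Step 4: corrected power.**

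| Outcome, difference/SD | Stated (n = 123) | ICC 0.01 (n = 93.75) | ICC 0.02 (n = 71.8) |
|---|---|---|---|
| Plaque 0.25/0.34 | 99 | 99.9 | 99.2 |
| Gingival 0.66/0.60 | 99 | >99.9 | >99.9 |
| Plaque 0.25/0.47 | 98 | 95.2 | 88.6 |
| Gingival 0.66/0.81 | 99 | >99.9 | 99.8 |
| Plaque 0.20/0.47 | 91 | 82.6 | 71.7 |
| Gingival 0.50/0.81 | 99 | 98.8 | 95.7 |

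**Step 5: where the conservative plaque row crosses 80%.** It needs 87.7 per arm, so the ICC at the crossing is (135/87.7 − 1)/44 = 0.012, between the plan's two values.

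**Step 6: the sentence at 135 per group.** Unadjusted, 135 gives 93.6% for the conservative plaque row. More than 90% is therefore true of 135 independent people per arm, but not of 135 people in three buildings of 45 at either ICC.

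**Side note.** The row labelled as 75% of the pilot effect uses 0.20, but 0.25 × 0.75 = 0.1875. With 0.1875 the lowest power is about 78% at ICC 0.01 and 66% at ICC 0.02. The table above keeps the plan's 0.20.

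**The case against.** The arithmetic itself has no good defence, but its consequence can be argued down.

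**Only one cell fails.** Of the twelve row-by-ICC combinations, only plaque 0.20/0.47 at ICC 0.02 is below 80%. At ICC 0.01 the range is 83–99%. This is correct, and both ranges should be reported. But 0.02 is one of only two ICCs that the plan assumes.

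**That row stacks pessimistic choices.** It takes a reduced effect, an upper-limit SD and full attrition. Plaque Score is a proportion, so an SD of 0.47 is close to the maximum of 0.50 if it describes scores rather than changes, which the plan does not say. With the table's pilot SD of 0.34, a difference of 0.20 keeps 98% or 94% power. This stands: the result does not show that Hypothesis 1 is underpowered under likely values. It shows that the protection the plan says its hedges provide is not there at ICC 0.02.

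**Attrition is charged at the wrong visit.** The comparison is at T1, whereas Section 4 expects "a final N of approximately 270 by the T3 measure", and Section 5.5.2 says: "If they withdraw after T1, we will include them in the T1 comparison". So 72% is close to a floor for T1. If the pilot's 15% attrition applied (an assumption; 51 per building), the effective size would be 153/1.50 = 102 or 153/2.00 = 76.5, and the row would have 86% or 74% power. With no losses at all it has 89% or 78%. The shortfall shrinks, but at ICC 0.02 it remains.

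**The supporting memo is not available.** Section 12.2 cites a memo of September 2016 that might show another derivation. It could explain 123, but it could not make 123 follow from the inputs printed in the section.

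**The models may do better than the t-test.** Covariates and repeated measures can add precision. That is possible, but no amount is shown, and six randomised buildings work in the other direction.

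**Conclusion.** The concern holds. On the plan's own inputs the effective sample size per arm is 94 (ICC 0.01) or 72 (ICC 0.02), not 123. Power across the six scenarios is about 83–99% or 72–99% respectively, against the stated 91–99%. The conservative plaque scenario falls below the 80% named in Section 12.2 once the ICC exceeds about 0.012. The Gingival Index conclusion is unaffected, at 95.7% or more throughout.

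These figures keep the plan's t-test, its differences and SDs, and 45 per building. They treat the effective sample as independent individuals, which is optimistic. With six buildings in three pairs, a building-level test has only 2 to 4 degrees of freedom. For the conservative plaque row, 4 df would give about 59% (ICC 0.01) or 49% (ICC 0.02), and 2 df about 37% or 31%, before any gain from matching. That is a caveat on the corrected range, not a replacement for it, because Section 12.4 does not specify a building-level test.

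**What to change.** 1. In Section 12.2, replace 123 per arm with 94 (ICC 0.01) and 72 (ICC 0.02), and show the design effect formula with m = 45.
2. Recompute the power column at both ICCs and restate the range as about 72–99% overall (83–99% at ICC 0.01).
3. If the T1 comparison is expected to include more than 45 per building, state that number and use it. Sixty per building gives 113 or 83 per arm.
4. Rewrite the 135-per-group sentence so that it agrees with the clustering adjustment, or label it as unadjusted.
5. In the Section 12.4 summary, remove or qualify the claim about the models' greater power, or show the calculation.
6. Add a sentence noting that six randomised buildings leave few degrees of freedom, so t-test power is optimistic.

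The cost is wording and one table column. No participants are added and no procedure changes. The lowest power the plan reports falls from 91% to about 72%.

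### The plaque row labelled as a 25% discount uses 0.20, a 20% cut of the tabulated 0.25; the stated rule gives 88% power at N=123 per group (90% if the pilot difference was 0.26), not 91%

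*Combined protocol and SAP*

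**What the plan says.** Section 12.2 gives one power table, headed "Sample size for a two-group t-test, using a two-sided α =0.05", with 123 per group in every row. Each primary outcome appears three times: with the pilot difference and pilot SD, with the pilot difference and the upper confidence limit of the SD, and with both a discounted difference and that upper limit.

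The text under the table describes the third version: the plan "decreased the observed effect size by 25% and 2) used the upper 95% CL of the standard deviation for calculations". The relevant rows read:

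- Plaque, no discount: "Pilot 0.25 0.47 (UCL) 0.53 123 98"
- Plaque, discounted: "Pilot*.75 0.20 0.47 (UCL) 0.42 123 91"
- Gingival, discounted: "Pilot*.75 0.50 0.81 (UCL) 0.62 123 99"

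From the table the text concludes: "Using N=123 per group, our power ranged from 91 to 99 for different scenarios". A little later it adds: "With N=135 per group our study still has more that 90% power". Between the rule and that last statement, the section names 80% as the power that the two hedges are meant to protect.

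**The concern.** The last two rows carry the label of a multiplication by 0.75, and the text confirms a 25% cut. Yet 0.20 is not three quarters of 0.25. The discounted plaque row is the only row in the table below 98, so it alone sets the lower end of the quoted range. It is also the row that shows the primary plaque outcome is adequately powered under the cautious assumptions on which the summary at the end of section 12.4 relies. If its input is more favourable than the stated rule allows, that reassurance is overstated.

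A second, smaller oddity concerns the N. Section 12.2 says that calculations use 123 per group rather than 135 because of clustering, but its closing power statement is given at 135.

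**Working it through.** **Inputs.** Two-sample t-test, two-sided alpha 0.05, 123 per group, plaque SD 0.47, pilot plaque difference 0.25, discounted difference 0.20 (table in 12.2); discount of 25% (text of 12.2); pilot plaque change from 84% to 58% and Gingival Index change from 1.2 to 0.54 (section 2.1).

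**Formula.** Effect size d = difference / SD. Noncentrality = d x sqrt(n/2). Power comes from the noncentral t distribution with 2n - 2 degrees of freedom.

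**1. Reproduce the printed figure.** 0.20 / 0.47 = 0.426; noncentrality 0.426 x sqrt(61.5) = 3.34; power 91.4%. With the printed effect size of 0.42 it is 90.7%. The 91 therefore follows from the row's own inputs. The other rows also reproduce to within about a point (for example, 0.25 / 0.47 gives 98.6% against a printed 98).

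**2. Check the discount.**

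- Gingival: 0.66 x 0.75 = 0.495, printed as 0.50. The rule is followed.
- Plaque: 0.20 / 0.25 = 0.80, a 20% cut. The rule gives 0.25 x 0.75 = 0.1875.

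**3. Can rounding explain it?** A value printed as 0.25 lies below 0.255, and 0.255 x 0.75 = 0.191, which prints as 0.19. To print as 0.20 after a 25% cut, the pilot difference must be at least 0.195 / 0.75 = 0.26. Rounding does not bridge the gap.

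**4. Apply the rule to 0.25.** 0.1875 / 0.47 = 0.399; noncentrality 0.399 x 7.84 = 3.13; power 87.6% (87.9% by the normal approximation). If the SD of 0.47 is itself rounded from anywhere between 0.465 and 0.475, power runs from 88.3% to 86.9%. Holding 91% would need about 137 per group.

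**5. Apply the rule to 0.26.** Section 2.1 gives 0.84 - 0.58 = 0.26. Then 0.26 x 0.75 = 0.195; 0.195 / 0.47 = 0.415; power 90.0%.

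**6. The N=135 statement.** At 0.1875 and 135 per group, noncentrality is 0.399 x sqrt(67.5) = 3.28 and power is 90.4%. At the printed 0.20 it is 93.6%.

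| Plaque difference | Origin | d | Power, N=123 | Power, N=135 |
|---|---|---|---|---|
| 0.20 | as printed | 0.426 | 91.4% | 93.6% |
| 0.195 | 0.26 x 0.75 | 0.415 | 90.0% | 92.5% |
| 0.1875 | 0.25 x 0.75 | 0.399 | 87.6% | 90.4% |

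**The case against.** The best defence is that 0.20 is right and 0.25 is the slip. The table's gingival difference of 0.66 matches section 2.1 exactly (1.2 - 0.54), so section 2.1 looks like the source of the pilot figures, and its plaque change is 0.26. Three quarters of that is 0.195, which prints as 0.20. This is plausible but not established. The undiscounted effect sizes were computed from 0.25 (0.25 / 0.34 = 0.74 and 0.25 / 0.47 = 0.53; with 0.26 they would be 0.76 and 0.55), and the memo that section 12.2 cites is not among the documents. The percentages in section 2.1 are also rounded: an underlying difference of 0.264, for example, would give 0.198 and 90.8%. So the defence identifies which cells might be wrong; it does not make the table consistent. It does rule out insisting on 88% as the only possible correction.

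Two stronger readings are tempting, and the documents support neither.

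- *A reader might infer that the correction falsifies the claim of more than 90% power.* That claim is made for N=135, and at 0.1875 it still holds (90.4%). What is wrong with it is the choice of N, which ignores the clustering adjustment made just above it.
- *A reader might infer that the hedged plaque scenario falls below 80%.* That happens only if N=123 is also replaced. With 45 per building, a design effect of 1 + 44 x ICC gives about 94 per group at ICC 0.01 and about 72 at ICC 0.02. Power at 0.1875 is then about 78% and 66%, but with the printed 0.20 left alone it is already about 83% and 72%. Most of that loss comes from the effective sample size, which is a separate question.

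**Conclusion.** Wrong as written, with a modest effect. The table's 0.25, its 0.20 and the stated 25% cut are mutually inconsistent. At 123 per group, the hedged plaque scenario has 87.6% power if 0.25 is the pilot difference and 90.0% if it is 0.26 taken at face value, against a printed 91. The shortfall is about 1 to 3.5 points.

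This takes N=123, the SD of 0.47 and the individual-level t-test as the plan gives them. On those terms the 80% target is met under either reading, and this error alone does not call for a change in sample size, design or analysis. The lower end of the quoted range needs restating, and so does the N at which the closing power statement is made.

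**What to change.** 1. State which pilot plaque difference was used, and reconcile section 2.1 with the table in 12.2.
2. If it was 0.25, correct the discounted plaque row to 0.19 (0.1875), effect size 0.40 and power 88, and restate the range as 88-99. If it was 0.26, correct the difference and effect size in the two undiscounted plaque rows, show the discounted row as 0.195 with power 90, and restate the range as 90-99.
3. Give the closing power statement at the cluster-adjusted N that section 12.2 says it uses, not at N=135.
4. If the effective sample size is itself revised, carry the corrected plaque difference into that calculation.

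The cost is restated figures and a slightly less favourable lower end to the range.
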